**Table 3: Detailed Schedule of Assessments for Cell Transplantation Visits (V6, V9 and V11)**

Estimated Time	06:00-14:00	12:00-14:00	14:00-16:00	16:00-18:00	19:00-21:00	08:00-10:00	12:00-14:00	
Time\ Procedure	Up to 6 hours before transplant	Hr. 0	Hr. 2 (±15 min)	Hr. 4 (±15 min)	Hr. 7 (±30 min)	Hr. 20 (±30 min)	Approximately Hr. 24 (±30 min)	Hr. ≥ 24-72 (before discharge ±30 min)
Admit to Inpatient Ward	√							
Body weight	√							
Physical Examination	√						√	
Vital signs 	√		√	√	√	√	√	√
12 lead ECG 	√						√ 	
ALSFRS-R	√							
Slow Vital Capacity (SVC)	√							
Neurological Examination	√							
Concomitant medication review 	√		√	√	√	√	√	√
Hematology 	√					√		
Blood biochemistry 	√					√		
Urinalysis 	√					√		
Coagulation 	√					√		
Blood collection for biomarkers 	√					√		
Cell Transplant IT 		√						
Retention of CSF sample		√						
Visual inspection of injection site			√			√ 		
Adverse events review 	√		√	√	√	√	√	√
C-SSRS 	√							
Assessment of blinding (Participant and Investigator) 								√
Discharge from Inpatient Setting								√

Abbreviations: ALS=Amyotrophic Lateral Sclerosis; ALFRS-R=ALS Functional Rating Scale–Revised; CSF=cerebral spinal fluid; C-SSRS=Columbia-Suicide Severity Rating Scale ECG=Electrocardiogram; IT=Intrathecal

- 1 Heart rate, Blood pressure, Respiration rate, Body temperature at the designated time-points. At 2, and 4 hours  $\pm$  15 minutes. At 8, 20 and 24 hours  $\pm$ 30 minutes.
- 2 ECG will be performed at Visits 6, 9 and 11 – Time Window: +/- 4 hours.
- 3 Concomitant medications and AEs will be monitored, and ongoing data will be collected throughout the study visit, as necessary.
- 4 Hematology: Complete blood count (Red blood cells with Indices, white blood cells with differential and platelet count, hemoglobin, hematocrit) - Time Window: +/- 30 min.
- 5 Blood Biochemistry: Sodium, Potassium, Calcium, Bicarbonate, blood urea nitrogen, Creatinine, Glucose, Chloride, Magnesium, Phosphorus, total protein, triglycerides, Total cholesterol, high-density lipoprotein, low-density lipoprotein, urea, total bilirubin, aspartate aminotransferase (glutamic oxaloacetic transaminase), alanine aminotransferase (glutamic pyruvic transaminase), alkaline phosphatase, uric acid - Time Window: +/- 30min.
- 6 Urinalysis - Specific Gravity, pH, glucose, protein, ketones, blood. Time Window: +/- 2 hours min.
- 7 Coagulation: Prothrombin time (PT), Partial thromboplastin time (PTT). Time Window: +/- 30 min.
- 8 Blood samples for analysis of T regulatory cells will be collected at V6 only
- 9 Time Window: +/- 1 hour
- 10 C-SSRS assessment will be performed at Visit 11 only.
- 11 At Visit 6 assessment of blinding is performed prior to discharge.

## **5. PLANNED ANALYSES**

### **5.1. Interim Analyses**

There are no interim analyses planned for this study.

### **5.2. Final Analyses**

Final Analyses will be performed after database lock.

## 6. GENERAL CONSIDERATIONS FOR DATA ANALYSES AND HANDLING

This section addresses the definitions, algorithms, imputations, and conventions that will apply to the analysis and handling of the data in general. Rules that are data specific will be addressed in the detailed discussions of individual sections below. This SAP and all TFLs created will use U.S. spellings.

### 6.1. General Summary Table and Individual Subject Data Listing Considerations

Summary tables and listings will include a “footer” providing explanatory notes that indicate as a minimum:

1. Date and time of output generation.
2. SAS program name, including the path that generates the output.
3. Any other output specific details that require further elaboration.
4. Page number in the format of Page X of Y

Summary tables will also include reference(s) to the subject data listing(s) that support the summary data.

In general, summary tables will be organized with respect to the 2 treatment groups, NurOwn® and Placebo. An overall total column may be included, where appropriate.

For this study, the order of drug presentation will be the investigational drug NurOwn® first followed by placebo.

The summary tables will clearly indicate the number of subjects with non-missing data along with an indication of the number of subjects with missing data.

If no data exist for any subjects for a given Table or Listing “No Data to display” will be displayed.

Summary tables for medications and medical conditions and AE verbatim (reported) terms are coded to preferred terms (PT) and body/organ systems are coded per standard dictionaries mentioned in [Section 6.3](#).

All data collected in the study will be presented in individual Subject Data Listings (unless agreed to with the agency to not create certain listings e.g. Laboratory listings, which tend to be very large). All listings will include subject ID and treatment group (group). Where applicable, listings will also include visit number, visit date, and days relative to the initiation of treatment.

When missing or partial dates are imputed, the listings will display both the missing or partial dates as well as the imputed dates.

Any data derived for analyses will also be included with the raw data in the listings and flagged as derived data.

## 6.2. General Post Text Summary Table and Individual Subject Data Listing Format Considerations

The default convention is to number tables and listings using a decimal system to reflect main levels of unique tables and listings and sub-levels of replicate tables and listings with two digits per level (e.g., Table XX.YY.ZZ. ...).

1. The first level number will be consistent with the corresponding CSR appendix in which the tables or listings will appear. For example, the post text tables usually occupy Appendix 14 and the individual subject data listings are in Appendix 16. All post text tables should have a main number level 14 and listings should have a main number level 16.2. The subject accounting and disposition table is usually first in the first section of the report and will be numbered Table 14.1. The supportive subject data listing would be Listing 16.2.1. A subset by sex table would have the number Table 14.1.2, etc.
2. Subject accounting, final disposition and baseline and demographic profile should appear as the second level number (Table 14.1 series). Efficacy should come next (14.2 series) followed by safety (table 14.3 series). Similar conventions will be applied to the subject data listings.
3. The Table/Listings title should be complete, accurate, and concise. The last line of the title should provide the analysis group being summarized (e.g., Modified Intent-to-Treat Population, Intent to Treat Population, Efficacy Evaluable Population or Safety Population). If possible, the units of measurement for data contained in the table can appear in parentheses to conserve space in the body of the table. For example, the summary of vital signs title could read “Summary of Sitting and Standing Blood Pressure (mmHg) and Heart Rate (bpm).” Whether in the title, footnotes or body of a table or listing, units must always be specified for all appropriate data unless obvious.
4. If possible, variables being summarized and statistics reported should appear in the left most column of a table. The next columns for treatment groups should report the data from left to right for the NurOwn®, placebo, and (optional) all treated subjects, respectively.
5. The definition of all derived variables and decodes for coded data must appear on the Table and Listings. Tables and Listings should be self-contained and all-relevant information to review the Table or Listing will either be in the titles, column or row headers, or in footnotes.

## 6.3. Data Management

Data from the study will be entered into Medidata RAVE, a validated electronic 21CFR Part 11 compliant database. Data review, coding, and logic, range, cross-form, and consistency checks will be performed to ensure quality of the data. Adverse events and medications will be coded using Medical Dictionary for Regulatory Activities (MedDRA) version 20.1 and the World Health Organization Drug Dictionary (WHODD) September 2017, respectively.

Derived datasets will be created using (SAS®) software.

Statistical programming and analyses will be performed using SAS® Version 9.4 or higher.

#### 6.4. Data Presentation Conventions

Continuous variables (e.g. age) are summarized using descriptive statistics (the number of subjects with available data, the mean, standard deviation (SD), first quartile (Q1), median, third quartile (Q3), minimum and maximum). Categorical variables (e.g. race) are summarized using counts and percentages. Percentages are calculated using the total subjects per treatment group with available data (overall or within relevant subgroup when appropriate). Summaries for discrete variables will include frequencies and percentages. Denominators used for computation of percentages will be indicated in footnotes on tables.

The following conventions will be applied to all data presentations and summaries.

- For continuous variables, all mean, Q1, median and Q3 values are formatted to one more decimal place than the measured value. Standard deviation values are formatted to two more decimal places than the measured value. Minimum and maximum values are presented with the same number of decimal places as the measured value. This rule may be modified to fit data in a given Table as long as the data displays relevant decimal places for interpretation of results.
- For categorical variables, the number and percentage of responses are presented in the form XX (XX.X%) where the percentage is in the parentheses and will be rounded to one decimal place.
- Date variables are formatted as DDMMYYYY for presentation. Time is formatted in military time as HH:MM for presentation.
- Wherever possible, data will be center, decimal or left aligned as appropriate to best display the data and column headers. Parenthesis will also be aligned appropriately for best display. This will be detailed in the mock shells.
- P-values, if applicable, will be presented to 3 decimal places. If the p-value is less than 0.001 then it will be presented as <0.001. If the rounded result is a value of 1.000, it will be displayed as >0.999.
- Unless otherwise stated, any statistical tests performed will use 2-sided tests at the 5% significance level.

#### 6.5. Analysis Populations

During the conduct of this study starting in February 2020 the pandemic due to COVID-19 impacted the US and some of the subject in-clinic visits for intrathecal administrations, efficacy or safety assessments were either delayed or cancelled. As of finalization of this SAP the COVID-19 pandemic is still ongoing and its impact is yet unknown. All subjects who continued in the study and were intended to receive treatments are receiving them with sometimes longer duration between visits due to travel restrictions, manufacturing and clinical site constraints. Phone visits were conducted as close to the planned visits to determine if subjects had AEs or there were changes to any CMs. Since the ALSFRS-R is validated to be performed over the

phone, these were conducted as close to the planned visits as possible. Protocol deviations due to COVID-19 are being captured and will be summarized in the clinical study report (CSR).

Prior to locking the database and unblinding the study, the impact of treatment delays due to manufacturing scheduling or due to COVID-19 will be assessed on the data collected and additional modifications to the populations below may be made. In addition, sensitivity analyses may be added including/excluding data collected that may have been impacted due to COVID-19.

### **6.5.1. Safety Population**

All safety analyses will be conducted on the Safety Population, which is defined as all participants who were randomized and had at least one treatment (transplantation) performed. The Safety Population will be analyzed based upon the treatment the subjects received.

### **6.5.2. Modified Intent to Treat (mITT) Population**

All efficacy analyses will be conducted using the mITT population which is defined as all subjects randomized, treated and having an assessment of pre-transplantation slope and post-transplantation slope, which requires at least three ALSFRS-R assessments: one pre-treatment ALSFRS-R assessment prior to the baseline assessment, a baseline assessment and one post-treatment assessment. Baseline will be the ALSFRS-R assessment at the first transplantation visit (Week 0, Visit 6) prior to treatment, or if this is unavailable, the most recent ALSFRS-R assessment prior to this time point. This will permit computing the slope from a linear regression pre- and post-treatment to get a rate of change in ALSFRS-R per month pre-treatment and post-treatment. The mITT population will be analyzed based upon the treatment groups subjects are randomized to. All efficacy analyses will be generated using the mITT population.

### **6.5.3. Intent to Treat (ITT) Population**

Analysis of the primary endpoint will also be conducted using the intent to treat (ITT) population which is defined as all participants who were randomized. The ITT population will be analyzed based upon the treatment groups subjects are randomized to.

### **6.5.4. Efficacy Evaluable (EE) population**

Analysis of the primary endpoint and key secondary endpoints will also be performed using the Efficacy Evaluable (EE) population which will be a subset of the mITT population. The exact criteria used to define the EE population will be finalized prior to locking the database and unblinding the study. This will be documented in the Appendix. The EE population will be analyzed based upon the treatment the subjects received. Any differences between treatment groups subjects were randomized to and treatments they received will be included in a listing and documented in the clinical study report.

## **6.6. Baseline Definition**

The baseline visit will be defined as the last non-missing measure prior to initiation of investigational treatment (first treatment at Visit 6, Week 0).

## 6.7. Derived and Transformed Data

### 6.7.1. Baseline Age

Subject's age in years will be calculated based on date of informed consent date using the following formula:

$$\text{Age (year)} = \text{FLOOR} ((\text{date of informed consent} - \text{date of birth})/365.25)$$

where FLOOR ( ) function returns the integer part of the result.

### 6.7.2. Study Day

If the date of interest (date of visit, date of start of medication, date of AE, etc.) occurs on or after the first dose date then study day will be calculated as (date of interest – date of first dose) + 1. If the date of interest occurs prior to the first dose date, then study day will be calculated as (date of interest – date of first dose). Study day 1 is the date of first dose and as per CDISC SDTMIG 3.2 requirements there is no study day 0.

### 6.7.3. Change and % Change from Baseline

Baseline is defined as the last non-missing observation prior to first study drug administration.

Change from baseline is calculated as (post-baseline result – baseline result).

If either the baseline or the post-baseline result is missing, the change from baseline is set to missing as well.

If the baseline result is missing or 0, or if the post-baseline result is missing, then % Change from Baseline will be set to missing at that visit.

### **6.8.2. Missing Start and Stop Dates for Prior and Concomitant Medication**

The following imputation rules will be used in this study:

Partial or missing start date for concomitant medication

1. Incomplete or partial start date will not be imputed if end date of concomitant medication is on or before treatment start date.
2. Incomplete or missing start date will be imputed as mentioned below if end date of concomitant medication falls after treatment start date (or if medication is ongoing at end of study for treated subjects).

Partial Start Date

1. Missing day - Impute the 1st of the month unless month and year is same as month and year of first dose of study drug then impute first dose date.
2. Missing day and month – impute 1st January unless year is the same as first dose date then impute first dose date.

Partial End Date

1. Missing day - Impute the last day of the month unless month and year is same as month and year of last dose of study drug then impute last dose date.
2. Missing day and month – impute 31st December unless year is the same as last dose date then impute last dose date.

### **6.8.3. Missing Start and Stop Dates for Adverse Events**

The following imputation rule will be used in this study:

Handling of missing/partial dates for Adverse Events

Partial/Missing Start Date

1. Missing day - Impute the 1st of the month unless month and year is same as month and year of first dose of study drug then impute first dose date.
2. Missing day and month – impute 1st January unless year is the same as first dose date then impute first dose date.

Partial/Missing End Date

1. Missing day - Impute the last day of the month unless month and year is same as month and year of last dose of study drug then impute last dose date.
2. Missing day and month – impute 31st December unless year is the same as last dose date then impute last dose date.

If an AE start date is completely missing or it is unclear whether the event occurred prior to or in the treatment period, the AE will be assumed to be treatment emergent (after initiation of first treatment).

If a medication end date is completely missing or it is unclear whether the medication was taken prior to or in the treatment period, the medication will be assumed to be taken during the treatment period as a “concomitant medication”.

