### 9.1. Adverse Event Preferred Term and Body/Organ System Summary Tables

#### 9.1.1. Summaries of Adverse Event Incidence Rates for All Subjects

All AEs will be coded to System Organ Class (SOC) and Preferred Term using the Medical Dictionary for Regulatory Activities (MedDRA®). Note, the terms AEs and TEAEs are used interchangeably in this SAP and unless otherwise specified refer to TEAEs.

A Treatment Emergent Adverse Event (TEAE) is defined as an AE that occurs for the first time after initiation of treatment or if it had occurred prior to treatment, it worsens in severity after initiation of treatment.

An overall summary by treatment group NurOwn® and Placebo that includes the number and percentage of subjects who experienced at least one TEAE for the following categories: TEAEs, serious TEAEs, treatment-related TEAEs, TEAEs by severity, TEAEs leading to treatment withdrawal, and TEAE leading to death and/or study discontinuation and procedure related TEAEs will be presented. When appropriate, a total column may appear as the last column.

Separate summaries with SOC and PT will be provided for the following categories of AEs:

- TEAEs
- TEAEs by severity
- Treatment-related TEAEs
- Serious TEAEs
- Procedure-related TEAEs
- Procedure-related TEAEs by severity
- All TEAEs excluding procedure-related TEAEs

The above summaries will include the number of events as well as number and percentage of subjects experiencing at least one TEAE in each SOC and Preferred Term. To count the number of participants with any TEAEs, a subject who experiences multiple TEAEs within the same SOC will be counted only once for that SOC (if the TEAEs are coded to the same Preferred Term). A subject who experiences multiple TEAEs coded to the same Preferred Term within the same SOC will be counted only once for that Preferred Term. The number and percentage of subjects experiencing any TEAE will also be provided. All percentages will use the number of subjects in the safety population within that treatment group as the denominator. In the summaries, SOCs will be sorted by alphabetical order and Preferred Terms within SOCs will be sorted by descending order of incidence in NurOwn® treatment group.

Treatment-emergent AEs will also be summarized by maximal severity (Mild, Moderate, Severe, or Potentially Life-Threatening). Summary table will include the number and percentage of subjects experiencing at least one TEAE in each SOC, Preferred Term, and severity.

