### **9.1.2. Missing and Partial AE Onset Dates**

The missing and partial AE onset dates will be imputed as described in [Section 6.8.3](#).

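### The partial-date rule for AE onset ignores the recorded end date, so an AE known to have ended before the first dose can be counted as treatment-emergent

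*SAP*

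**What the plan says.** **AE start dates (SAP 6.8.3).** Day missing: "Missing day - Impute the 1st of the month unless month and year is same as month and year of first dose", in which case the first dose date is used. Day and month missing: "impute 1st January unless year is the same as first dose date then impute first dose date".

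**AE end dates (SAP 6.8.3).** Day missing: "Impute the last day of the month unless month and year is same as month and year of last dose of study drug", in which case the last dose date is used. Day and month missing: "impute 31st December unless year is the same as last dose date then impute last dose date".

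**Fallback (SAP 6.8.3).** "If an AE start date is completely missing or it is unclear whether the event occurred prior to or in the treatment period", the event is taken to be treatment-emergent.

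**Medications (SAP 6.8.2).** The start-date rule carries a condition that 6.8.3 lacks: "Incomplete or partial start date will not be imputed if end date of concomitant medication is on or before treatment start date". The end-date rule is worded as in 6.8.3.

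**Use in the safety analysis.** SAP 9.1.2 adds no condition: "The missing and partial AE onset dates will be imputed as described in" Section 6.8.3. SAP 9.1.1 says that a TEAE "is defined as an AE that occurs for the first time after initiation of treatment", or one that was present before treatment and worsens after it starts.

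**The concern.** AEs are collected from screening onward (SAP 9), and the pre-treatment period lasts up to 20 weeks (SAP 4.1). Events that began and resolved before the first dose will therefore be in the database. If such an event has a partial start date in the first-dose month or year, the rule moves its onset to the first dose even though the recorded end shows that it was already over. It then enters the TEAE tables, and the derived record starts after it ends.

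Counting an event as treatment-emergent when its timing is unknown is a sound convention. Here the timing is known, and the rule overrides it. Safety is one of the two primary objectives, so the tables should not contain events that the trial's own data place before treatment.

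The end-date rule has a mirror-image fault. It uses the last dose as the latest plausible end, but participants are followed for 12 weeks after it (SAP 4.1), so AEs and medications can start later than the end date they are given.

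**Working it through.** The documents give no figure for this point, so there is none to reproduce. The check applies the rules literally.

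**Worked dates.** Assume a first dose on 20 May 2019. The third dose is at Week 16, so the last dose is 20 May + 112 days = 9 September 2019. An event dated on the day of first dose is taken as treatment-emergent, which is the evident purpose of moving it there.

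| Case | Recorded start | Recorded end | Imputed date | Result |
|---|---|---|---|---|
| A | May 2019 | 10 May 2019 | start 20 May | TEAE; starts 10 days after it ended |
| B | 2019 | 15 March 2019 | start 20 May | TEAE; starts 66 days after it ended |
| C | 14 September 2019 | September 2019 | end 9 September | ends 5 days before it started |
| D | 5 November 2019 | 2019 | end 9 September | ends 57 days before it started |

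Under the medication rule in 6.8.2, the start dates in A and B would not be imputed, because the end falls before the first dose. The fallback sentence in 6.8.3 does not rescue A or B: the start is not completely missing, and the recorded end makes the timing clear.

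**How far the rules reach.** The following assumptions are illustrative and are not in the documents: first dose equally likely on each day of 2019, last dose 112 days later, each AE lasting 5 days, onset days equally likely.

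*Start dates.* AEs beginning 140 to 6 days before the first dose resolve before it: 135 onset days × 365 dose dates = 49,275 combinations.
- Only the day missing: an AE is moved if its onset is in the first-dose month. For a first dose on day d of the month there are d − 6 such onset days (none if d ≤ 6). Summing over d gives 325 for a 31-day month, 300 for a 30-day month and 253 for February. Total: 7 × 325 + 4 × 300 + 253 = 3,728, and 3,728 / 49,275 = 7.6%.
- Day and month missing: an AE is moved if its onset is in the first-dose year. The count is 39,420, and 39,420 / 49,275 = 80.0%.

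*End dates.* AEs beginning 1 to 79 days after the last dose: 79 × 365 = 28,835 combinations.
- Only the day missing: 3,748 / 28,835 = 13.0% get an end before onset.
- Day and month missing: 25,280 / 28,835 = 87.7%.

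Each percentage applies only to AEs whose date is partial in that way. None is a share of all AEs.

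**The case against.** **The tables will hardly change.** Protocol 1.8.2 has the eCRF record the date and time of onset and of resolution, and AEs are reviewed at every visit from Visit 2. Partial dates should be few, and year-only dates fewer. This stands: it limits the size of the point, but it does not make the rule right.

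**The TEAE definition already excludes these events.** It can be argued that an event with a recorded end before the first dose did not first occur after treatment began, whatever start was imputed. The SAP does not say which source prevails, however, and 9.1.2 sends the programmer to 6.8.3 without qualification. Coded as written, cases A and B are TEAEs.

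**Listings keep the recorded dates.** SAP 6.1 has listings show both the partial and the imputed date. A reader of the listings could therefore find the error, but nothing corrects the summary tables.

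Four stronger readings are tempting, and the documents do not support them:
- *The rule sweeps marrow-aspiration events into the TEAE tables.* Protocol 1.5.5.1 places the first dose about 5–6 weeks after aspiration, that is 35–42 days. Two dates in one calendar month are at most 30 days apart, so with only the day missing the rule cannot reach an event at or just after aspiration. On the Week -4 timing given in Protocol 1.3.1 and SAP 4.1 (28 days), an event on the day of aspiration shares the first-dose month only if the first dose falls on day 29, 30 or 31. Otherwise a year-only start date would be needed.
- *The long pre-treatment window means that many AEs are misclassified.* Its length is a share of calendar time, not of AEs.
- *The treatment comparison is biased.* The rule is the same in both arms, and nothing in the documents suggests that partial dates differ between them.
- *The end-date rule distorts safety results.* The tables in SAP 9.1.1 and the relatedness summary that follows count incidence, severity, seriousness and relatedness. None uses an AE end date or duration.

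**Conclusion.** The start-date rule in SAP 6.8.3 is wrong as written. It can turn an AE with a recorded end before the first dose into a TEAE with an onset after its own end, and neither 9.1.1 nor 9.1.2 prevents this. The conclusion rests on a literal reading of 6.8.3 and on counting an event dated on the first-dose day as treatment-emergent.

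The effect is probably small. The documents give no rate of partial dates, so the number of AEs affected cannot be computed. The error can only add to TEAE counts, and no direction of bias between arms is shown.

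The end-date defect, shared by 6.8.2 and 6.8.3, is secondary: it yields impossible imputed dates in listings but changes neither TEAE status nor a planned AE table. This is a minor point, worth correcting because the correction is so short.

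**What to change.** 1. Add to SAP 6.8.3: *If the recorded end date (full or partial) shows that the AE ended before the first dose, the AE is not treatment-emergent and its start is not moved to the first dose date; impute the 1st of the month (or 1 January) instead.* Case A then starts on 1 May and case B on 1 January, both before treatment. Events whose timing is truly unclear keep the treatment-emergent default.

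2. In SAP 6.8.2 and 6.8.3, replace the last-dose exception for end dates with: *impute the last day of the recorded month (or 31 December of the recorded year), no later than the date of death if applicable, and never before the start date.* Case C then ends on 30 September and case D on 31 December.

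Do not add an end-of-study cap. SAEs are followed to resolution or stabilization (Protocol 1.8.1.5), and AEs that a site learns of within 12 weeks of the last transplant are recorded even after a participant has discontinued (Protocol 1.8.5.2). For such events a cap could place the end before the start, or before the recorded month.

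The cost is a few words in the SAP and matching lines in the date-derivation program, with no new data. SAP Section 2 already provides for changes before database lock and unblinding, captured in an appendix.
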